5.4 Removal of Patients from Study

A patient will be considered to have completed the study when he or she has completed all study visits through the final visit. Every patient has the right to discontinue study participation at any time at his/her own request, or may be withdrawn at any time at the discretion of the investigator for safety, behavioral, or administrative reasons. Criteria for early termination include, but are not limited to, poor adherence to study medication (less than 70% of study medication consumed), loss of health insurance coverage, and safety issues related to study-related or non-study related adverse events.

If a patient has a clinical necessity to alter their standard PD medications, the patient will be withdrawn from the trial so that changes may be made, except that occasional additional doses of carbidopa/levodopa will be allowed if needed to address periodic worsening of parkinsonian symptoms. If a patient is withdrawn due to an adverse event, the event will be followed, when possible, until resolution. Patients who withdraw from the study may be replaced, but withdrawn patients will not be re-entered into the study.

All data generated up to the time of discontinuation from the study will be analyzed and the reason(s) for discontinuation will be recorded.

5.5 Screen Failures & Re-screening

Subjects who fail screening because they do not meet inclusion criteria or because of certain exclusions, e.g. concurrent use of a prohibited medication, may be re-screened after 4 weeks at the discretion of the investigator.

6. TREATMENTS

6.1 Investigational Drug

Study medication, to include 5-mg and 10-mg suvorexant and matching placebo, will be provided by Merck. The active medication will be suvorexant 10-15 mg qhs. The research pharmacist at EvergreenHealth will be responsible for packaging and labeling individual bottles, which will be done in a standard prescription bottle with child-proof cap. The pharmacist will dispense the active or placebo medication at randomization (Office Visit 2, start of Treatment Period 1) and again Office Visit 4 (start of Treatment Period 2). This will include a 4-week supply of 10 mg tablets (suvorexant or matching placebo) and a 2-week supply of 5 mg tablets (suvorexant or matching placebo). The subject will use the 5-mg tablets only if instructed to do so at Phone Visit 2 or Phone Visit 5. In this case, the 5-mg tablets will be taken concurrently with the 10-mg tablets to achieve the titration dose of 15 mg QHS. To prevent confusion, the bottle of 5-mg tablets will be packaged in a sealed bag with a label stating, "Open only if instructed to do so on _____." In the blank, the coordinator will write in the date of Phone Visit 2 or 5, as appropriate. In addition, a pictorial depiction of the titration schedule will be provided to the subject.

At Office Visit 3 (start of washout period), placebo will be dispensed that matches what the subject was taking at the end of Treatment Period 1. For example, if the subject titrated to 15 mg at Phone Visit 2, both a 10-mg and 5-mg placebo will be dispensed at Office Visit 3. If the subject remained on 10 mg for the duration of Treatment Period 1, only a 10-mg placebo will be dispensed.

An extra 7-day supply of medication will be provided for each study period to allow a window for scheduling of appointments.

6.2 Randomization and Blinding

Following confirmation of eligibility, an eligible patient will be randomized in a 1:1 randomization scheme to receive suvorexant or placebo. Randomization will occur at the research pharmacy of EvergreenHealth using a computer-generated randomization list. The pharmacist will maintain a codebook indicating the treatment allocation of each subject. Study medication will be delivered by the research pharmacist to the research study staff from the research pharmacy (a separate locked room containing only research medications). The investigating physicians, nurse, research coordinator, and study subjects will be blinded as to treatment arm until the code is broken. The randomization code may be broken by the investigator only in a medical emergency. In the event of a medical emergency, the reasons for breaking the code will be documented carefully. The subjects will receive identical appearing active or placebo study medication tablets, with identification known only to the research pharmacist.

6.3 Concomitant Therapy

All concomitant therapy will be documented. Concurrent (defined as “within 14 days of screening”) use of medications listed in section 5.3 will be prohibited. Medications that are likely to influence sleep or sleepiness may not be initiated between screening and study completion. They may be continued with no dose changes during the study.

6.4 Treatment Compliance

Patients will be asked to return all unused medication and all medication bottles, including empty bottles, at each visit and at the end of the study. The quantity of medication dispensed and returned will be documented.

7. DESCRIPTION OF ASSESSMENTS

7.1 Safety Monitoring

Safety will be monitored by physical examination, vital signs, laboratory evaluation, and adverse event (AE) reporting with particular inquiry on falls and next-day drowsiness.

7.1.1 Physical Examination

A general physical examination will be performed at Office Visit 1 (Screening Visit), Office Visit 3 (Start of Washout Period) and Office Visit 5 (Final Visit). This exam will include, at minimum, HEENT, heart, lungs, abdomen, musculoskeletal, and neurologic systems. Subjects with a range of health conditions that may put the patient at risk for adverse outcomes will be excluded, as listed under Section 5.2, Exclusion Criteria.

7.1.2 Laboratory Evaluations

All subjects will undergo baseline testing with CBC, CMP, albumin, and INR. Child-Pugh score will be calculated if there is a history of liver failure or if AST or ALT are elevated. Those subjects with a Child-Pugh score > 10 will be excluded. CBC and CMP will be assessed at Office Visit 3 (start of washout period) and Office Visit 5 (final visit) to ensure stability.

7.1.3 Pregnancy Status

All pre-menopausal women will have pregnancy screening with urine hCG at all Office Visits (1-5). A positive urine hCG at screening will result in exclusion from the study; a positive urine hCG at any other office visit will result in discontinuation of the study drug and withdrawal of the subject from the study.

7.1.4 Adverse Events

Subjects will be monitored for adverse events throughout the trial. The occurrence of adverse events will be ascertained by observation, telephone monitoring and questioning by the investigator or coordinator. Safety assessments will consist of monitoring and recording all adverse events, including serious adverse events. Falls and next-day drowsiness will be specifically queried.

An adverse event (AE) is any symptom, physical sign, or medical condition that emerges during the study or, if present at screening, worsens during the study, regardless of the suspected cause. Adverse events include adverse drug reactions, illness with onset during the study, exacerbations of pre-existing conditions or clinically significant changes in physical examination or significantly abnormal objective test findings. Medical conditions/diseases present before starting study treatment are only considered adverse events if they worsen after starting study

treatment. All adverse events will be recorded and graded as mild, moderate or severe by the principal investigator in accordance with general guidelines of clinical research, outlined here:

- **MILD:** An event that causes transient or minimal symptoms and that does not interfere with daily activities.
- **MODERATE:** An event that causes symptoms sufficient to interfere with but not prevent daily activities.
- **SEVERE:** An event that prevents normal, everyday activities.

Adverse events will also be classified by their relationship to the study medication by the principal investigator in accordance with general guidelines of clinical research, outlined here:

- **Definitely Unrelated:** The AE is definitely not related to the drug. This designation is reserved for those events that do not follow a reasonable temporal sequence following drug administration (e.g. occur prior to study treatment) or for those events that cannot be even remotely related to study participation.
- **Unlikely related:** There is no reasonable association between the study treatment and the suspected event and the event could have been produced by the patient's clinical state or other therapy administered to the patient.
- **Possibly related:** The suspected AE may or may not follow a reasonable temporal sequence from study treatment administration but seems to be the type of reaction that cannot be dismissed as unlikely. The event could have been produced or mimicked by the patient's clinical state or other therapy administered to the patient.
- **Probably related:** The suspected AE follows a reasonable temporal sequence from study treatment administration, abates upon discontinuation of the treatment, and cannot be reasonably explained by the known characteristics of the patient's clinical state or other treatments.
- **Definitely related:** The suspected AE follows a reasonable temporal sequence from study treatment administration, abates upon discontinuation of the treatment, and, if appropriate, resumes upon re-introduction of the treatment. Additionally, the suspected AE cannot be reasonably explained by the known characteristics of the patient's clinical state or other treatments.

The principal investigator and all other research staff except the research pharmacist will be blinded towards randomization of active drug versus placebo until after completion of study.

7.1.5 Serious Adverse Events

A serious adverse event (SAE) is any AE that meets one or more of the following criteria:

- Is fatal or life-threatening
- Requires hospitalization or prolongs a current hospitalization
- Results in persistent or significant disability/incapacity
- Is a congenital anomaly
- Requires medical or surgical intervention to prevent one of the above outcomes

If any SAE occurs, the treatment status of the subject(s) may be revealed, as clinically indicated. If a patient discontinues medication use due to an AE, the event will be followed, when possible, until resolution. No interim analysis of safety data is planned. However, the frequency of AEs will be under continuous scrutiny during the trial with comparison to AE rates that have been recorded in published PD drug trials.

7.1.5.1 Serious Adverse Events Reporting

The FDA will be informed of SAEs as soon as possible or within 15 calendar days. In addition, the Investigator will notify the FDA of any unexpected fatal or life-threatening experience associated with the use of the drug as soon as possible, or within 7 calendar days, by telephone or facsimile. When the principal investigator has determined that an SAE requires reporting to the FDA (unexpected and possibly related to study drug), the following actions will be taken:

- Telephone the FDA immediately (day of awareness) if the case involves a reportable death or a life-threatening event.
- Complete FDA Form 3500.
- Send the completed Form 3500 to the FDA (preferably by fax at [name]) within the timelines mentioned above.
- Attach the photocopy of all examinations, medical notes and records related to the SAE and document the dates these were made. For laboratory results, include the laboratory normal ranges. For hospitalizations, include Admission H&P, Discharge Summary, Consultative reports, and other similar notes. In the case of a fatal event, if an autopsy is performed, a copy of the autopsy report will be provided when it becomes available.

7.1.6 Special Note on Suicidality as an Adverse Event

In the event that the administration of the C-SSRS at follow-up visits (Phone Visits 2 or 5 or Office Visits 3 or 5) reveals worsening suicidal ideation relative to baseline or any suicidal behavior since the last administration, the subject will be withdrawn from the study. Intervention will be initiated as deemed appropriate in the clinical judgment of the investigator and may include referral to the subject's primary care provider, referral to the in-house psychology group at EvergreenHealth Neuroscience Institute, emergency referral to the EvergreenHealth Emergency Department, or activation of Emergency Medical Services by dialing 9-1-1. Suicidal ideation requiring hospitalization will be considered an SAE, and any suicidal behavior will be considered an SAE, with reporting requirements as per section 7.1.5.1.

7.2 Efficacy Assessment Based on Polysomnogram

7.2.1 Sleep Efficiency

The primary outcome measure will be sleep efficiency as measured by PSG, defined as (total sleep time / total time in bed) * 100%.

7.2.2 Wake After Sleep Onset

WASO is defined as total time spent awake after first epoch of sleep and before final awakening. This will be a secondary outcome measure.

7.2.3 Latency to Persistent Sleep

LPS is defined as total time between lights out and first epoch of sleep. This will be a secondary outcome measure.

7.2.4 Muscle Tonicity

Muscle activity during REM sleep will be recorded as a measure of REM Behavior Disorder.

7.3 Efficacy Assessment Based on Clinical Rating Scales

7.3.1 Insomnia Severity Index

The ISI is a 7-question survey assessing symptoms of insomnia. Maximum score is 28, with higher scores indicating greater severity. The ISI has been validated for use in insomnia research (Bastien 2001). This will be performed at Office Visits 2, 3, 4, and 5, and will be a secondary outcome measure.

7.3.2 Epworth Sleepiness Scale

The ESS is an 8-question survey assessing symptoms of sleepiness. Maximum score is 24, with higher scores indicating greater severity. The ESS has been validated for use in the general population (Johns 1991) and in PD (Hagell 2007). This will be performed at Office Visits 2, 3, 4, and 5, and will be a secondary outcome measure.

7.3.3 Subject's Global Impression of Change

The SGIC will be assessed by asking a single question at Phone Visits 2 and 5 and Office Visits 3, 4, and 5: "Since baseline (when first starting this study), how have your sleep symptoms changed?" Answers will be on a 7-point scale: 1 = much improved; 2 = somewhat improved; 3 = minimally improved; 4 = no change; 5 = minimally worse; 6 = somewhat worse; and 7 = much worse. This will be performed at Phone Visits 2 and 5 and at Office Visits 3, 4, and 5, and will be a secondary outcome measure.

7.3.4 Clinician's Global Impression of Change

The CGIC will be assessed by the investigator at Office Visits 3, 4, and 5 using a similar question: "Since baseline (when first starting this study), how have the subject's sleep symptoms changed?" Answers will be on a 7-point scale: 1 = much improved; 2 = somewhat improved; 3 = minimally improved; 4 = no change; 5 = minimally worse; 6 = somewhat worse; and 7 = much

worse. This will be performed at Office Visits 3, 4, and 5, and will be a secondary outcome measure.

7.3.5 Montreal Cognitive Assessment

The MoCA is an assessment of global cognition using a 30-point scale and investigating performance in visuospatial ability, executive function, naming, attention, language, abstraction, delayed recall, and orientation. It will be performed at Office Visits 1, 3, 4, and 5, and will be used as a secondary outcome measure to assess the effect of suvorexant on cognition in PD.

7.3.6 Beck Depression Inventory-II

The BDI is a 21-question assessment of symptoms of depression, with higher scores indicating more severe depression, to a maximum score of 63. This scale has been validated for use in assessing depression in Parkinson disease (Leentjens 2000). It will be performed at Office Visits 2, 3, 4, and 5, and will be used as a secondary outcome measure to assess the effect of suvorexant on depression in PD.

7.3.7 Beck Anxiety Inventory

The BAI is a 21-question assessment of symptoms of anxiety, with higher scores indicating more severe depression, to a maximum score of 63. This scale has been validated for use in assessing depression in Parkinson disease (Leentjens 2011). It will be performed at Office Visits 2, 3, 4, and 5, and will be used as a secondary outcome measure to assess the effect of suvorexant on anxiety in PD.

7.3.8 Movement Disorder Society's Unified Parkinson Disease Rating Scale (MDS-UPDRS)

The MDS-UPDRS is a widely used and validated (Goetz 2008) rating scale in PD, assessing non-motor symptoms of PD (part I), motor symptoms of PD (part II), motor signs of PD on physical exam (part III), and symptoms of motor complications in PD (part IV). Part I includes two questions about sleep symptoms: question 1.7 (sleep problems) and question 1.8 (daytime sleepiness). All questions are rated on a 5-point scale (0-4), with higher scores indicating greater severity. The maximum score on part I is 52, on part II it is 52, on part III it is 132, and on part IV it is 24. Total score, the score on part I, the score on question 1.7, and the score on question 1.8 will be secondary outcome measures. The scores on parts II, III, and IV will be used as safety measures to ensure no worsening of motor symptoms, motor signs, or motor complications. Part III will be performed at Office Visit 1; Parts I, II, and IV will be performed at Office Visit 2; and the full scale (parts I-IV) will be performed at Office Visits 3, 4, and 5.

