1.6.2 Secondary Hypotheses

- On nights of PSG, total hours of sleep and WASO as measured by a wearable sleep monitor will not be significantly different from those values as measured by PSG.
- Suvorexant will not worsen motor symptoms or non-motor symptoms of PD compared to placebo; motor signs and motor and non-motor symptoms will be assessed by the Movement Disorder Society's Unified Parkinson Disease Rating Scale; specific non-motor symptoms will be assessed by the Beck Depression Inventory, the Beck Anxiety Inventory, and Montreal Cognitive Assessment; REM behavior disorder will be assessed by muscle tonicity during PSG.

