3.4 Secondary Hypotheses

1. On nights of PSG, total hours of sleep and WASO as measured by a wearable sleep monitor will not be significantly different from those values as measured by PSG.
2. Suvorexant will not worsen motor symptoms or non-motor symptoms of PD compared to placebo.

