8.4 Baseline and Demographic Characteristics

The following characteristics will be summarized descriptively for placebo and drug groups:

- Demographics (age, gender, race)
- Parkinson disease characteristics at baseline (disease duration, date of onset, initial symptom, modified Hoehn and Yahr stage in the ON state, and MDS-UPDRS part 3 score in the ON state)
- Levodopa-equivalent daily dose (LEDD), calculated according to published formulae (Tomlinson 2010, Rytary Prescribing Information, Duopa Prescribing Information).

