8.5 Efficacy Analysis

Analysis of primary and secondary outcome measures will include:

- Summary statistics (n, mean, standard deviation, median, minimum and maximum) at baseline, Office Visit 3 and Office Visit 5 by treatment.
- For clinical rating scales, summary of % change from baseline to Office Visit 3, from baseline to Office Visit 5, and from Office Visit 4 to Office Visit 5, by treatment
- For PSG variables, summary of % change from PSG 1 to PSG 2 and from PSG 1 to PSG 3, by treatment

- For wearable sleep monitor, summary of % change in total hours of sleep and WASO. Mean over the week prior to Office Visit 2 (baseline) will be compared to the mean over the final week of Treatment Period 1 and to the mean over the final week of Treatment Period 2. Mean over the week prior to Office Visit 4 (during washout) will be compared to the mean over the final week of Treatment Period 2. This will be done by treatment arm.
- Significance testing

Outcome measures will be compared between groups using analysis of covariance (ANCOVA) or other method as deemed appropriate by the consulting statistician. Demonstration of superiority will depend on achieving statistical significance for the primary endpoint. Level of significance will be defined as $p = 0.05$. All statistical tests will be two-sided.

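### No motor-specific score has a planned suvorexant-placebo comparison, and the no-worsening hypothesis has no margin or confidence-interval rule behind it

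*Combined protocol and SAP*

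**What the plan says.** Secondary hypothesis 2 (section 3.4) is a claim of no harm: "Suvorexant will not worsen motor symptoms or non-motor symptoms of PD compared to placebo". Section 1.6.2 names the instruments: "motor signs and motor and non-motor symptoms will be assessed by the Movement Disorder Society's Unified Parkinson Disease Rating Scale". It adds the BDI, BAI and MoCA for specific non-motor symptoms, and muscle tone on PSG for REM behavior disorder.

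Section 7.3.8 then divides the MDS-UPDRS. On one side, "Total score, the score on part I, the score on question 1.7, and the score on question 1.8 will be secondary outcome measures"; section 1.10.3 lists the same four. On the other, "The scores on parts II, III, and IV will be used as safety measures to ensure no worsening of motor symptoms", with motor signs and motor complications named in the same sentence. The full scale is collected at Office Visits 3, 4 and 5.

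Section 8.5 opens with "Analysis of primary and secondary outcome measures will include", followed by descriptive summaries by treatment and significance testing. It continues: "Outcome measures will be compared between groups using analysis of covariance (ANCOVA) or other method", the alternative being left to the consulting statistician. Tests are two-sided at 0.05. Section 8 has no subsection on safety data. The safety monitoring list in section 7.1 (physical examination, vital signs, laboratory tests, adverse events) does not mention the MDS-UPDRS. No margin, interval rule or definition of worsening appears anywhere.

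**The concern.** There are two gaps, and they compound each other.

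First, the scores that measure motor function most directly carry a stated purpose, to make sure that motor function does not get worse, but have no stated analysis. The one planned comparison containing them is the Total score, which also contains Part I and its two sleep items. If suvorexant improves sleep, as the trial hopes, Part I falls, and that fall can hide a rise in Parts II-IV.

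Second, a test of difference answers a different question from the one hypothesis 2 asks. Failure to reach p < 0.05 is expected both when there is no harm and when harm is moderate and the sample small. Without a margin or a rule for reading the confidence interval, the plan does not say what result would support the hypothesis.

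At stake is the answer to secondary objective 2. Section 8.2 gives safety in this population as a purpose of the trial, and section 2.1 says that measuring motor and non-motor severity matters in insomnia studies in PD.

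**Working it through.** **1. Which measures are compared**

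| Measure under hypothesis 2 | Role in the plan | Between-treatment comparison in 8.5 |
|---|---|---|
| MDS-UPDRS Total | Secondary outcome (1.10.3, 7.3.8) | Yes |
| Part I, items 1.7 and 1.8 | Secondary outcome (1.10.3, 7.3.8) | Yes |
| Parts II, III, IV | Safety measure (7.3.8) | None stated |
| MoCA, BDI, BAI | Secondary outcome (1.10.3) | Yes |
| REM muscle tone | Secondary outcome (1.10.2) | Yes |

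**2. Motor content of the Total**

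Section 7.3.8 gives these maxima: 52 (Part I), 52 (Part II), 132 (Part III) and 24 (Part IV).

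- Total maximum: 52 + 52 + 132 + 24 = 260.
- Parts II-IV: 52 + 132 + 24 = 208, and 208/260 = 80%. Part III alone: 132/260 = 51%.
- Part I: 52/260 = 20%. Items 1.7 and 1.8 are each scored 0-4, so together they can move the Total by up to 8 points.

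For illustration only, a 3-point rise in Part III with a 3-point fall in Part I leaves the Total unchanged.

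**3. What 20 pairs can show**

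The plan gives no power, effect size or SD. Section 8.2 bases the sample size of 20 on a level-of-evidence convention, so there is no planned figure to reproduce. Results below are in units of SDd, the SD of the within-subject suvorexant-minus-placebo difference.

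Inputs: n = 20, each subject on both treatments (8.2); 1:1 randomization (6.2), taken as 10 per sequence; two-sided alpha 0.05 (8.5); df = 20 - 2 = 18 after adjusting for period.

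The period-adjusted estimate averages the two sequence means of the drug-minus-placebo difference. Its variance is (SDd²/10 + SDd²/10)/4 = SDd²/20.

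- 95% CI half-width = t(0.975, 18) × SDd/√20 = 2.101/4.472 × SDd = 0.47 SDd.
- Power comes from the noncentral t distribution with noncentrality d√20, where d is the true worsening in SDd units:

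| True worsening (SDd) | Power | Chance of a non-significant result |
|---|---|---|
| 0.2 | 14% | 86% |
| 0.3 | 25% | 75% |
| 0.5 | 56% | 44% |
| 0.66 | 80% | 20% |

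Using 19 df gives a half-width of 0.468 SDd and changes power by less than 0.3 percentage points. If only 16 subjects complete, the worsening detectable with 80% power rises to about 0.75 SDd.

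**4. Reading**

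A true worsening of half an SDd would give a non-significant result about 44% of the time. Even an observed difference of exactly zero would leave a worsening of up to 0.47 SDd inside the interval.

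**The case against.** The strongest reply is that motor function is compared: the Total is a named secondary outcome, 80% of its maximum is motor, and 8.5 tests it. That stands. A reader might infer from 7.3.8 that the motor half of hypothesis 2 receives no comparison at all, and the Total rules that reading out. What remains is that no motor-specific score is compared and that Part I can mask a motor change.

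A reader might also infer that the trial will report no worsening whenever p > 0.05. No section says so; 8.5 links significance only to superiority on the primary endpoint. The companion hypothesis in 3.4, on the wearable monitor, is itself phrased as the absence of a significant difference, which makes that reading a real risk. The documented defect is still a missing rule, not a wrong one.

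The plan is not limited to tests. Section 8.5 includes descriptive summaries by treatment and permits another method. On a lenient reading, its percentage-change summary for clinical rating scales could cover Parts II-IV, but the lead-in restricts the list to primary and secondary outcomes. The open clause names no non-inferiority method. Nor is a difference model incapable of addressing harm: its confidence interval can do so once a rule is stated.

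Motor harm would not go unobserved. Adverse events include exacerbations of existing conditions, falls are specifically asked about (7.1.4), and a clinical need to alter PD medication leads to withdrawal with the reason recorded (5.4). None of this replaces a randomized comparison of motor scores.

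Finally, 8.4 summarizes the baseline "MDS-UPDRS part 3 score in the ON state", and no such condition is given for later visits. A reader might infer noisier follow-up examinations. The documents do not say that those examinations are done OFF, they require stable PD regimens, and they give no figure for added noise, so this forms no part of the point.

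**Conclusion.** The point holds in this form: no motor-specific score has a planned treatment comparison, and hypothesis 2 has no margin or interval rule, so a non-significant result would not support it. With 20 complete pairs the 95% CI half-width is about 0.47 SDd, and power is about 56% at 0.5 SDd and 80% at 0.66 SDd. These figures assume 10 subjects per sequence, approximately normal differences and no dropout.

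The documents give no variance for any MDS-UPDRS part, so the results cannot be turned into scale points without an outside assumption, and none is made here.

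Low power alone is no fault in a study that calls itself exploratory. Pilot status does not, however, resolve a hypothesis that an imprecise result could appear to confirm. Because this is a secondary hypothesis in a pilot, the change is one the sponsor should make; the primary analysis is not affected.

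**What to change.** In section 8.5:

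1. Add MDS-UPDRS Parts II, III and IV to the scores compared by treatment.
2. For each hypothesis 2 measure (Parts I-IV, MoCA, BDI, BAI, REM muscle tone), report the period-adjusted within-subject suvorexant-minus-placebo difference with its 95% CI.
3. State each conclusion as the largest worsening that the interval does not exclude: the upper limit where higher scores are worse, the lower limit for the MoCA. Do not conclude no worsening from p > 0.05. Alternatively, reword hypothesis 2 as an estimation aim.

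Formal non-inferiority margins are not needed in this pilot. With a true difference of zero and one-sided alpha 0.025, 20 pairs give 80% power only for a margin of about 0.66 SDd.

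The cost is SAP wording and a few more table rows, using data already scheduled for collection. The downside is that the report may have to say that a worsening of a given size is not excluded.
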